## 9 ASSESSMENTS

### 9.1 Efficacy Assessments

#### 9.1.1 Model for End-Stage Liver Disease

The model for end-stage liver disease (MELD) is employed in the evaluation of hepatic function and the assessment of prognosis. MELD is calculated based on variables including the international normalised ratio (INR), serum creatinine, and serum bilirubin.

A MELD score  $\geq 18$  (within 24 hours of presentation) is considered a good predictor of 90 day mortality in patients with AH.

MELD will be assessed at Visit 1/Screening, Visit 2/Baseline, Visit 3/Day 3, Visit 4/Day 5, Visit 5/Day 7, Visit 6/Day 14, Visit 7/Day 21, Visit 8/Day 28/Early Termination and Visit 9/Day 90/Follow up.

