### **12.8.2 Primary Variables**

The primary efficacy variable will be change in MELD score from baseline to Day 28. This change in MELD score and its difference between treatment groups will be estimated using a General Linear Repeated Measures Model with treatment arm, baseline MELD value, visit and treatment arm by visit interaction as factors. The primary analysis will be based on the FAS and repeated for the PPS as a supportive analysis.

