3 SAMPLE SIZE

To discover an effect size of 0.54 (=Difference in means/standard deviation) in MELD change from baseline with 80% power, 55 patients per group are necessary under ideal assumptions using the t-test for independent samples (alpha=0.05, two-sided).

To take deviations from ideal parametric conditions and drop-outs into account, 60 patients per group will be randomised.

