6.11.1 Primary Analysis

Percentage change in MELD score from baseline up to and including day 28 will be assessed by modelling change from baseline with a mixed-model repeated measures (MMRM) analysis, using the FAS, including terms for treatment group, visit, treatment-by-visit interaction as fixed effects and the baseline MELD value as a covariate. The adjusted treatment least squares (LS) means and adjusted mean LS difference between the active dose and placebo will be presented along with 95% confidence intervals (CI) and p-value for the day 28 timepoint. Early termination data will be entered into the model at the next scheduled visit following the date of termination, not at day 28.

F-tests from PROC MIXED will be based on Kenward-Roger's adjusted degrees of freedom. The following variance/covariance matrix structures for the repeated visits within a patient will be assessed: Compound symmetry, 1st order autoregressive, Toeplitz and unstructured. The variance/covariance matrix structure that results in the smallest Akaike's information criterion (AIC), indicating the best model fit will be selected.

Assumptions of normality will be assessed visually using diagnostic plots. Should assumptions of normality not hold the model will be fitted to the change from baseline of log-transformed data. Should the assumptions behind the model still not hold an alternative approach to the analysis will be decided following the BDRM and will be detailed in a SAP amendment.

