6.12.1.1 Analysis

Change in total bilirubin from baseline up to and including day 28 will be assessed with an MMRM analysis, using the FAS, including terms for treatment group, visit, treatment-by-visit interaction as fixed effects and the baseline total bilirubin value as a covariate. The adjusted treatment means and adjusted mean difference between the active dose and placebo will be presented along with 95% CI and p-value at days 7, 14, 21 and 28.

The modelling process described in section [6.11.1](#) will be followed.

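### The primary MMRM fits one baseline-MELD slope for all visits; a baseline-by-visit term would probably sharpen the Day 28 contrast at almost no cost

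*SAP*

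**What the plan says.** SAP 6.11.1 models MELD change up to and including Day 28 on the FAS, "including terms for treatment group, visit, treatment-by-visit interaction as fixed effects and the baseline MELD value as a covariate". It reports the treatment difference "along with 95% confidence intervals (CI) and p-value for the day 28 timepoint". Protocol 12.8.2 describes a "General Linear Repeated Measures Model with treatment arm, baseline MELD value, visit and treatment arm by visit interaction as factors". Neither text lets the baseline effect differ by visit.

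The SAP does not list the visits that enter the model. Protocol 9.1.1 schedules MELD after baseline at Days 3, 5, 7, 14, 21 and 28, which makes six visits sharing one slope.

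The AIC step chooses only among covariance structures ("Compound symmetry, 1st order autoregressive, Toeplitz and unstructured"), and the named diagnostics concern normality. The sensitivity analyses in SAP 6.11.2 refit the same mean model. The same form recurs in the continuous secondary and exploratory models, for example total bilirubin in SAP 6.12.1.1: "including terms for treatment group, visit, treatment-by-visit interaction as fixed effects and the baseline total bilirubin value as a covariate".

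The sample size (SAP 3, Protocol 12.3) rests on an unadjusted t-test: "effect size of 0.54 (=Difference in means/standard deviation) in MELD change from baseline with 80% power, 55 patients per group are necessary".

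**The concern.** The response is change from baseline. At Day 3 a patient's MELD is still close to the baseline value, so the slope of change on baseline is near zero. By Day 28 the correlation with baseline has usually weakened and the slope is usually more negative. A single slope is a compromise between the two. Under an unstructured covariance the fit weights it towards the early visits, where the residual variance is smallest. Day 28 then receives a slope that is too shallow, and baseline variation that could have been removed stays in the error.

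What is at stake is the standard error of the one contrast the trial tests. The Day 7, 14 and 21 estimates (SAP 6.12.8) come from the same fit. So does the Day 28 imputation that places patients lost to follow-up in level 4 or 5 of the ordinal outcome (SAP 6.13.7).

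**Working it through.** **Inputs from the documents.** Model terms and Day 28 test (SAP 6.11.1); visits (Protocol 9.1.1); d = 0.54, two-sided alpha 0.05, 55 per group, 60 randomised (SAP 3).

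**Assumed, because the documents do not give them.** Baseline to Day 28 correlation r from 0.3 to 0.8; Day 28/baseline SD ratio k from 1 to 2; correlation decaying with lag; measurement noise 0 to 8%; response on the absolute-change scale. Baseline variance is set to 1.

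**Step 1: the plan's own figure.** Noncentral-t power for d = 0.54 at 55 per group is 0.8014, which matches the table in Protocol 12.3. At 60 per group with no loss it is 0.835.

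**Step 2: slope at visit t.** b_t = r_t × k_t − 1. With r = 0.5 and k = 1, b at Day 28 is 0.5 − 1 = −0.50. With 3% noise, b at Day 3 is −0.10.

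**Step 3: pooled slope c.** Under unstructured covariance, c minimises log|Σ + (b − c)(b − c)′|. Under compound symmetry it is the mean of the six slopes. In the example, c = −0.15 under unstructured covariance.

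**Step 4: Day 28 variance ratio, common slope against baseline-by-visit.** Ratio = 1 + (b28 − c)² / [k²(1 − r²)]. In the example, 1 + 0.35² / 0.75 = 1.163. That is 16% more variance and √1.163 = 1.08, or 8% more SE.

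**Step 5: power at 55 per group, with d = 0.54 on the SD of unadjusted change.** In the example the unadjusted variance is 0.75 + 0.25 = 1.
- Unadjusted: 0.801.
- SAP model: 0.54/√(0.75 × 1.163) = 0.578, power 0.852.
- With baseline-by-visit: 0.54/√0.75 = 0.624, power 0.900.

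**Step 6: a selection from the grid, 8% noise (UN = unstructured, CS = compound symmetry).**

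| r | k | b28 | c (UN) | Ratio UN | Ratio CS | Power, SAP model (UN) | Power, with interaction |
|---|---|---|---|---|---|---|---|
| 0.5 | 1.0 | −0.50 | −0.20 | 1.116 | 1.057 | 0.866 | 0.900 |
| 0.7 | 1.0 | −0.30 | −0.14 | 1.051 | 1.025 | 0.844 | 0.861 |
| 0.5 | 1.25 | −0.38 | −0.15 | 1.045 | 1.020 | 0.828 | 0.844 |
| 0.3 | 1.5 | −0.55 | −0.19 | 1.063 | 1.027 | 0.830 | 0.852 |
| 0.5 | 1.5 | −0.25 | −0.10 | 1.013 | 1.006 | 0.810 | 0.815 |
| 0.7 | 1.5 | 0.05 | −0.05 | 1.009 | 1.003 | 0.799 | 0.802 |
| 0.8 | 1.5 | 0.20 | −0.03 | 1.064 | 1.025 | 0.796 | 0.820 |
| 0.5 | 2.0 | 0.00 | −0.04 | 1.000 | 1.000 | 0.801 | 0.801 |
| 0.8 | 2.0 | 0.60 | 0.02 | 1.237 | 1.084 | 0.806 | 0.881 |

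Over the whole grid the ratio is 1.00 to 1.26 under unstructured covariance (√1.26 = 1.12, so SE up to 12%) and 1.00 to 1.11 under compound symmetry. The power gain is 0 to about 7.5 points. The loss vanishes when the Day 28 slope is close to the early slopes. Growth in SD brings this about at middling correlations. When the SD doubles and the correlation stays high, the slope turns positive and a loss returns.

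**Step 7: simulation check.** Unstructured model, 60 per group, 1,000 runs per setting, for r/k of 0.5/1, 0.5/1.25, 0.7/1, 0.7/1.5 and 0.3/1. Variance ratios were 1.19, 1.07, 1.09, 1.00 and 1.22 with complete data. They were 1.11, 1.05, 1.08, 1.00 and 1.28 with about 22% missing at random at Day 28. Bias was at most 0.02 SD under either model.

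**Step 8: entry limit.** MELD at baseline must be at least 18 (Protocol 7.2), which narrows baseline variance but not Day 28 variance. With an assumed latent SD of 6, mean 20 to 26 and correlation 0.5 to 0.7, truncation lowers the ratio from 1.09–1.17 to 1.04–1.11, about 2 to 5% of SE.

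**The case against.** The best defence is that nothing in the documents shows the slopes differ. No SD, correlation or slope is given, some plausible settings show no loss, the entry limit shrinks the loss, and AIC may select compound symmetry, where it is smaller. Power was planned for an unadjusted t-test, so any baseline adjustment is a bonus. All of this stands. It limits what can be said about size and certainty. It does not argue against a term that costs almost nothing.

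Three stronger readings are tempting, and the documents do not support them.

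- **That a chance baseline imbalance biases the result.** With an assumed baseline SD of 5, a two-SE imbalance is 2 × 5 × √(2/60) ≈ 1.8 points. In an unfavourable setting (Day 28 slope −0.59, common slope −0.22) that leaves 0.37 × 1.8 ≈ 0.67 points unadjusted. Under randomisation such imbalances average to zero. They are the source of the extra variance in Step 4, not a second harm.
- **That the trial falls short of 80% power.** The 80% belongs to the unadjusted test. At 55 per group, power under the SAP model never fell below 0.796 anywhere in the grid. With about 22% missing, far above the 5/60 = 8.3% allowed for, simulated power at r = 0.7, k = 1.5 was 0.736 with the common slope and 0.733 with the interaction. In that setting the missing patients are the cause, not the slope.
- **That every model citing 6.11.1 needs the change.** The algebra concerns change scores. Nothing was calculated for the binary models (SAP 6.12.2, 6.12.7, 6.12.10) or the ordinal ones (6.12.11, 6.13.7).

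**Conclusion.** The point holds as a cheap improvement in efficiency. SAP 6.11.1 and Protocol 12.8.2 agree with each other, and both omit baseline-by-visit. Under-adjustment at Day 28 is the likely direction, but the documents do not establish it. Under the assumptions above, the Day 28 SE is 0 to 12% larger than it need be with unstructured covariance. The upper end needs either low correlation with constant SD or high correlation with doubled SD, and baseline truncation pulls towards the lower end.

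The validity of the test is not in question. Randomisation protects the type I error rate in principle (it was not simulated), and the simulated bias was negligible. The size of the gain for the continuous secondary endpoints was not calculated. It depends on their own correlations and SDs.

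**What to change.** Before unblinding:

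1. Add a baseline MELD by visit interaction to the primary MMRM in SAP 6.11.1. Keep the Day 28 LS-mean difference as the primary estimate.
2. Put matching text in Protocol 12.8.2, or record the departure in SAP 6.25.
3. Make the same change in the continuous change-from-baseline MMRMs that reuse the process (SAP 6.12.1, 6.12.3 to 6.12.6, 6.12.9 and 6.13.2 to 6.13.6). The Day 7, 14 and 21 MELD estimates in 6.12.8 follow automatically.
4. Leave the binary and ordinal models as they are; this argument does not reach them.
5. Settle the response scale first. SAP 6.11.1 says percentage change is assessed by modelling change, and the baseline slope depends on which is meant.

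The cost is five extra parameters (six slopes instead of one) with about 120 patients. At worst this adds about 1% to the Day 28 variance: the lowest ratio seen was 0.99. It also needs a text change. SAP 6.2 already provides for a SAP amendment before database lock; changing the protocol text would go through the amendment process in Protocol 13.1. No new data or patients are needed.

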### 9.2.5 Clinical Laboratory Safety Tests: Haematology, Serum Biochemistry, and Coagulation

Blood and urine samples will be taken as per the Study Flow Chart (Appendix 1 and 2) for routine haematology, serum biochemistry, coagulation. All samples will be analysed in a central laboratory.

Haematology: Full blood count to include red cell count, haemoglobin, haematocrit, white cell count, differential white cell count, platelet count and reticulocyte count.

Serum biochemistry: Urea (blood urea nitrogen (BUN)), creatinine, uric acid, total bilirubin, indirect and direct bilirubin, sodium, bicarbonate potassium, phosphorus, calcium chloride, alkaline phosphatase (ALP), AST, ALT, AST:ALT ratio, gamma GT, albumin, total protein, total cholesterol, triglycerides, glucose, C-reactive protein (CRP), plasma caeruloplasmin (screening only).

Coagulation: PT (prothrombin time), INR and APTT (activated partial prothrombin time)

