2.4 Visit Structure

During the study, 8 visits to the clinic are scheduled after the screening visit (Visit 1): one at the start of the comparative treatment period (Baseline/Visit 2) and six in the comparative treatment period (Visit 3/Day 3, Visit 4/Day 5, Visit 5/Day 7, Visit 6/Day 14, Visit 7/Day 21, Visit 8/Day 28 or Early Termination).

A final safety follow-up visit (Visit 9/Day 90) will be conducted on Day 90.

Both the pilot and main, double-blind, phase will follow the same structure.

Full details of the visit structure and scheduled assessments are detailed in the study protocol section 8 Study Conduct and Appendices 1 and 2.

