6.12.2.1 Descriptive summaries and listing

The number and percentage of patients showing and patients not showing a 25% reduction of bilirubin at days 7, 14, 21 and 28 will be presented by treatment group.

6.12.3 Change in serum Cytokeratin-18 M30/M65 from baseline to Day 7, 14, 21 and 28

Change in serum cytokeratin18-M30/M65 from baseline up to and including day 28 will be assessed with an MMRM analysis, using the FAS, including terms for treatment group, visit and treatment-by-visit interaction as fixed effects and the baseline serum cytokeratin18-M30/M65 value as a covariate. The adjusted treatment means and adjusted mean difference between the active dose and placebo will be presented along with 95% CIs and p-value at days 7, 14, 21 and 28.

The modelling process described in section 6.11.1 will be followed.

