6.12.6.2 Descriptive summaries and listing

MDF score observed values, absolute change from baseline and percentage change from baseline will be listed and summarised by treatment group and visit.

6.12.7 Proportion of patients showing a 25% reduction in MELD score from baseline to Day 7, 14, 21 and 28

The proportion of patients showing at least a 25% reduction in MELD score at days 7, 14, 21 and 28 will be compared between treatment groups using a MMRM logistic regression model.

At each visit, patients with $\geq 25\%$ reduction from baseline will be assigned a value of 1 (indicating 25% reduction achieved) while patients with a $< 25\%$ reduction will be assigned a value of 0 (indicating 25% reduction not achieved).

The model will include treatment, visit, treatment-by-visit interaction as fixed effects and baseline MELD score as a covariate.

The variance/covariance matrix structure that results in best model fit will be selected using the process described in section [6.11.1](#).

The adjusted LS estimate for the treatment odds of achieving the endpoint and treatment odds ratio (DS102:Placebo) along with corresponding 95% CIs and p-value (corresponding to the treatment odds ratio) will be presented at days 7, 14, 21 and 28.

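### Choosing the primary MMRM covariance by AIC, with three of four candidates assuming equal variance at every visit, leaves the Day 28 error rate dependent on unknown visit SDs and correlations: typically 6–7% if residual SD grows 10–20%

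*SAP*

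**What the plan says.** SAP 6.11.1 models change in MELD up to Day 28 with treatment, visit, their interaction and baseline MELD. It tests the Day 28 contrast at two-sided 5% with Kenward-Roger degrees of freedom. The candidate covariance structures are "Compound symmetry, 1st order autoregressive, Toeplitz and unstructured", and the smallest AIC on the trial data decides. No heterogeneous-variance version, robust standard error or default structure is named.

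SAP 2.4 lists the post-baseline visits in the treatment period as "Visit 3/Day 3, Visit 4/Day 5, Visit 5/Day 7, Visit 6/Day 14, Visit 7/Day 21, Visit 8/Day 28": six visits, spaced two days apart at first and seven days apart later.

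Protocol 12.8.2 fixes the model terms ("with treatment arm, baseline MELD value, visit and treatment arm by visit interaction as factors") but says nothing about covariance.

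SAP 3 sizes the trial by a t-test: "55 patients per group are necessary under ideal assumptions using the t-test for independent samples", raised to 60 randomised per group.

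Other models borrow the rule. The continuous endpoints do so by a sentence such as the one in SAP 6.12.3 ("The modelling process described in section 6.11.1 will be followed"). The repeated logistic and ordinal models do so by one such as that in SAP 6.12.7 ("The variance/covariance matrix structure that results in best model fit will be selected using the process described in section").

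**The concern.** Compound symmetry, AR(1) and Toeplitz all assume the same variance at Day 3 as at Day 28. If patients spread out over the month, a pooled variance understates the Day 28 variance. The Day 28 standard error is then too small and the test rejects too often. Kenward-Roger adjusts the standard error and degrees of freedom within the chosen structure; it does not correct the structure itself.

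Unstructured is on the list, so AIC can escape the problem, but it pays for 21 parameters against 2 or 6. With modest variance growth the penalty often outweighs the gain in fit. The error rate of the primary p-value then depends on quantities nobody knows until the outcome data are seen.

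**Working it through.** **Plan's own figure.** Noncentral-t power at d = 0.54, two-sided 5%, is 0.8014 at 55 per group and 0.7940 at 54. The stated 55 reproduces and is not affected by this point.

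**AIC penalty.** With six visits the covariance parameters number 2 (compound symmetry), 2 (AR(1)), 6 (Toeplitz) and 6 × 7 / 2 = 21 (unstructured). AIC adds 2 per parameter. Unstructured therefore wins only if it lowers −2 × restricted log-likelihood by more than 2 × (21 − 2) = 38 against the two-parameter structures, or 2 × (21 − 6) = 30 against Toeplitz.

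**Size if an equal-variance structure is always kept.** Assumption: residual SD rises linearly in days from 1 at Day 3 to r at Day 28, and data are complete. The pooled variance is roughly the mean of the six visit variances, so

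error ≈ 2Φ(−1.96 × √(mean variance) / r).

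For r = 1.2 the SDs are 1, 1.016, 1.032, 1.088, 1.144 and 1.2. Their mean variance is 1.1716, and √1.1716 / 1.2 = 0.902. The standard error is about 10% too small and the error is 2Φ(−1.768) = 7.7%. The same formula gives 6.4% at r = 1.1, 9.0% at 1.3 and 11.3% at 1.5. A 20% jump at Day 28 only gives mean variance 6.44 / 6 = 1.0733, SE ratio 0.863 and error 9.1%. These are the values before AIC switches some trials to unstructured.

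**Size under the SAP rule.** Null trials were simulated with 60 per arm, complete data, REML fits of all four structures, smallest AIC, and a full Kenward-Roger test at Day 28. Six correlation patterns were used (constant, or by visit number), with 2,000 trials per cell.

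| SD ratio, Day 28 / Day 3 | Equal-variance structure kept | Error, AIC choice |
|---|---|---|
| 1.0 | about 99% | 4.9–5.0% |
| 1.1 | 96–99% | 6.1–6.3% |
| 1.2 | 56–92% | 6.3–7.3% |
| 1.3 | 10–67% | 5.3–7.2% |
| 1.4 | 0–33% | 5.0–6.4% |
| 1.5 | 0–10% | 5.0–5.4% |

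Unstructured on the same data gave 4.9–5.0%. The average Day 28 standard error under AIC choice was about 5% too small at ratio 1.1 and 5–8% at 1.2. Further runs with other patterns and Satterthwaite degrees of freedom gave 5.7–6.5% at 1.1, 6.1–7.7% at 1.2 and 5.0–7.2% at 1.3.

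**Correlation decaying by actual days.** The grid had 30 cells, with 0–40% visit-level noise and MELD SD constant or growing 25%. Error was 6.3–6.9% in 8 cells and 5.0–5.9% in the other 22. The 8 cells had 20–40% noise and an SD ratio of 1.12–1.37. In the 12 cells with 0–10% noise, unstructured was chosen in at least 98% of trials and error was 5.0–5.1%.

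**Other shapes.** An SD that shrinks 10–20% gave 3.3–4.2%. A 20% jump at Day 28 only gave 8.2%.

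**Dropout.** At ratio 1.2, runs with different assumed dropout mechanisms gave between 6.1% and 7.8%. Because this varies with the settings, it is not used for the headline. Across all runs, including those with dropout, unstructured fixed in advance gave 4.1–5.8%, consistent with 5% within simulation noise.

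**The case against.** The strongest objection is that nothing in the documents shows the harmful case applies. The rule is pre-specified, unstructured is a candidate, and AIC adopts it when heterogeneity is large. By-visit-number correlation treats a two-day gap like a seven-day gap; by-day decay is more natural, and most of that grid sits below 6%. One set of runs with noise on by-day correlation reached only 4.7–6.0%, so that boundary depends on the settings. Two features may also favour the harmless case. The variance of a change from baseline may be small at Day 3 and grow strongly, and Protocol 9.2.5 says "All samples will be analysed in a central laboratory", which may limit visit-level noise. If only Days 7 to 28 were modelled, the error at 10–30% growth would be about 5.3–6.9%. All of this stands, and it is why the point is conditional.

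A second objection is that SAP 6.11.1 lets a failed model assumption be handled by an amendment after the blinded data review. That route exists, but the only named check is normality plots; nothing is specified that would detect unequal visit variances.

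A reader might also infer that the single baseline slope compounds the problem. It does not. A common slope does not bias the Day 28 contrast, and its larger precision losses (11–26% of variance) arose only where AIC chose unstructured and error was 5.0–5.1%. Baseline MELD-by-visit is a separate, optional precision choice.

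**Conclusion.** The concern holds conditionally. With residual SD growth of about 10–30% and correlation that is constant, by visit number or noisy, the Day 28 test runs at about 5–7%, typically 6–7% at 10–20% growth. Two stronger readings are tempting. One is that the primary test is inflated as planned; the documents give no visit SDs or correlations, so they cannot show that. The other is that the error is 5% everywhere outside this region; a shrinking SD makes the test conservative, and a late jump takes it to about 8%. What is established is that the error rate under AIC selection depends on unknown variance and correlation patterns, while one of the plan's own candidates stays near 5% throughout. The excess is usually one to two points in an exploratory phase II trial, so this is an improvement worth considering and not a flaw that undermines the design.

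**What to change.** In SAP 6.11.1, replace the AIC selection for the primary analysis with:

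> An unstructured covariance matrix with Kenward-Roger degrees of freedom will be used; only if it fails to converge, the first of heterogeneous Toeplitz, then first-order ante-dependence, that converges will be used.

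Both fallbacks allow a separate variance at each visit, with 6 + 5 = 11 parameters each. Make the change before unblinding. Protocol 12.8.2 does not specify covariance, so its model terms are unaffected. The MELD contrasts at Days 7, 14 and 21 (SAP 6.12.8) and the sensitivity analyses (SAP 6.11.2) follow automatically because they use the primary model.

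Keep the present AIC text as its own paragraph, stated to apply to the secondary and exploratory models that cross-refer to 6.11.1, so that those references are not emptied. Those analyses are descriptive under SAP 6.14 and need no other edit.

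Cost: 21 covariance parameters and a little power if variances really are equal. At d = 0.54 with 55 per arm and complete data, power is 80.07% with unstructured against 80.35–80.39% with AIC choice, about 0.3 points. Adding baseline-by-visit as well, which is not proposed here, would make it about 0.4. The cost under dropout has not been quantified.
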